#### **8.5 AE Reporting and Follow-up**

Adverse events will be reported from the time of first study drug administration until 30 days after the last dose of study drug. All ongoing AEs will be followed until resolution, the subject is lost to follow-up, subject death, or until 30 days after last dose of study treatment, whichever is earlier. In case the AE has not completely resolved up to 30 days after last dose of study treatment, the final outcome of these ongoing AEs will be captured as "Not Recovered/Not Resolved" or "Recovering/Resolving", whichever is applicable. Any new AEs occurring more than 30 days after last dose of study treatment will not be captured unless related to study drug.

For specific instructions on identifying and reporting SAEs, see Sections [8.6](#) and [8.7](#).

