- t. One pre-treatment tumor tissue biopsy will be collected during screening (Cycle 1 Day 1 to 28 days). If a pre-treatment biopsy was collected within 28 days, tumor sections can be provided. One on-treatment tumor tissue biopsy will be collected at Week 3 (7 to 1 days prior to Cycle 2 Day 1). An additional tumor tissue biopsy may be collected at the time of progression. All tumor biopsies will be collected from the same non-target lesion, if feasible. Exceptions will be made with Medical Monitor approval for tumors that are inaccessible.
- u. The screening immunogenicity sample should be drawn within 14 days prior to Day 1 Cycle 1. No immunogenicity sample will be drawn at pre-dose on Cycle 1 Day 1. Immunogenicity samples will be drawn at pre-dose on Cycle 2 Day 1, pre-dose on Day 1 of all odd-numbered cycles thereafter (e.g., Cycles 3, 5, 7, etc.), and at End-of-Treatment and Follow-up.
- v. Tumor assessment at screening then every 8 weeks ( $\pm 7$  days) and End-of-Treatment (unless scan done within 4-weeks). To ensure comparability, the baseline radiographs/scans and subsequent radiographs/scans to assess response should be performed using identical techniques. In the event of a partial response (PR) or complete response (CR), confirmatory radiographic imaging should be completed at least 4 weeks from imaging showing a CR or PR. If the subject discontinues treatment for a reason other than Progressive Disease, imaging will be conducted every 3 months until progressive disease is noted or start of new treatment.
- w. Any new or clinically significant changes in the subject's medical and/or cancer history that occur immediately after the first dose of drug will be recorded as AEs. All AEs, including serious AEs (SAEs), will be recorded immediately after the first dose of study drug until 30 days after the last dose of study medication. An SAE related to study procedures or study conduct must be reported to Nektar Therapeutics if it occurs prior to first dose of study drugs. SAEs must be reported as described in Section 8.7 of the protocol. Treatment-related AEs ongoing at the post-treatment visit should be followed to resolution or until the Investigator considers them "chronic" or "stable".

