### **5.3 Removal of Subjects from Study Therapy or Assessment**

Subjects may choose to discontinue the trial at any time, for any reason, and without prejudice to further treatment.

Subjects may stop participating in or be withdrawn from the study for any of the following reasons, but are to be followed according to the procedures section for progression of disease and for safety until resolution or permanent sequelae of all toxicities attributable to the study drug.

- Subject has progressive disease,
- Occurrence of a clinically significant AE found to be unacceptable by the Investigator;
- Subjects who need more than 6 weeks to recover from treatment-related toxicities;
- Symptomatic deterioration,
- Achievement of maximal response,
- Noncompliance of the subject with protocol-mandated procedures based on agreement of both the Investigator and Sponsor;
- Continued participation is no longer in the subject's best interest in the opinion of the Investigator;
- If a female subject becomes pregnant, administration of the study drug must be discontinued immediately;
- Withdrawal of Consent;
- The study is terminated by the Sponsor.

In the event of a subject's withdrawal, the Investigator will promptly notify the Sponsor and make every effort to complete the Early Termination assessments specified in the Schedule of Assessments (Section 1.2).

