### **6.5 Post-treatment Period**

The EOT/Early Termination visit is to occur within 30 days (+ 10 days) after last dose of study drug.

Subjects who reach the EOT visit without radiographic disease progression must continue to undergo immunogenicity testing and radiological assessment at the interval of every 3 months ( $\pm 7$  days) until either disease progression per RECIST version 1.1 or the start of a new anti-cancer therapy. Subjects will also be followed every 3 months ( $\pm 7$  days) for survival until death, lost to follow-up, study termination by Sponsor, or 3 years have passed since the subject's first dose.

For any toxicity the Investigator attributed to study drug, the Investigator will assess the subject to determine whether the toxicity resolved or worsened. Information on whether the toxicity resolved or worsened must be entered into the eCRF.

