### 6.10.2 Immune-related Adverse Events

Permanently discontinue NKTR-214 for:

- Grade 2 or 3 immune-related AEs (irAEs) that do not improve to Grade 0 or 1, except endocrinopathies managed with replacement hormones
- Grade 3 irAEs that recur at  $\geq$  Grade 3
- Grade 3 immune-related pneumonitis, colitis, hepatitis, pancreatitis

- Grade 4 irAEs, except endocrinopathies managed with replacement hormones
- Any uveitis event

Subjects who need more than 6 weeks to recover from treatment-related toxicities should be removed from study treatment.

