### **8.7 Serious AE Reporting**

SAEs with an onset within 30 days after the subject's last dose of study treatment, but before initiation of a new antineoplastic treatment, will be reported to Nektar Therapeutics Drug Safety within 24 hours of when the site becomes aware of the event. It is anticipated that some patients will experience disease progression before study discontinuation, and the disease progression may result in hospitalization or death. Adverse events leading to hospitalization or death typically are considered serious and require reporting on a serious adverse event form. In addition, disease progression per se is already captured as an efficacy endpoint. Where possible,

- It is unlikely that any additional information can be obtained (e.g., subject or health care practitioner refuses to provide additional information; lost to follow-up after demonstration of due diligence with follow-up efforts)
- The subject dies or is lost to follow-up.

All ongoing SAEs assessed as “unrelated” to study medication will be followed until resolution or until 30 days after last dose of study medication, whichever is earlier. In the case where an unrelated SAE has not completely resolved up to 30 days after last dose of study treatment, the final outcome of these ongoing SAEs will be captured as “Not Recovered/Not Resolved” or “Recovering/Resolving”, whichever is applicable.

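### Protocol 8.5 ends follow-up of related AEs at 30 days, against footnotes w/v and 5.3; SAP 6 and 10.2, read literally, report unresolved related TEAEs as completed durations ending at study exit

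*Protocol*

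**What the plan says.** **Follow-up of AEs.** Protocol 8.5: "All ongoing AEs will be followed until resolution, the subject is lost to follow-up, subject death, or until 30 days after last dose", whichever comes first. An AE still open at that point gets a final outcome of not recovered or recovering. The same section adds: "Any new AEs occurring more than 30 days after last dose of study treatment will not be captured unless related to study drug".

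Other parts of the protocol set a different rule for drug-related events:

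- Table 1 footnote w (Part 1) and Table 2 footnote v (Part 2): "Treatment-related AEs ongoing at the post-treatment visit should be followed to resolution or until the Investigator considers them" chronic or stable.
- Section 5.3, for subjects who stop or are withdrawn: follow-up "for safety until resolution or permanent sequelae of all toxicities attributable to the study drug".
- Section 6.5: "For any toxicity the Investigator attributed to study drug, the Investigator will assess the subject to determine whether the toxicity resolved or worsened", with the answer entered in the eCRF.

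**Duration of AEs.** The protocol synopsis and SAP 10.2 plan a summary of toxicity duration. SAP 10.2 defines duration as stop date minus start date plus 1, averages repeat episodes within a subject, and sends incomplete dates of related TEAEs to SAP 6. SAP 6 replaces a completely missing stop date, for any AE, with the date of discontinuation from the study. Neither section mentions ongoing events, censoring or the recorded outcome.

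**The concern.** A site with a non-serious related AE open at day 30 cannot obey all of these rules. Section 8.5 lets it close the event; the footnotes and 5.3 tell it to continue. Sites may differ, and the late course of some related toxicities would go unrecorded.

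The SAP issue is separate. An AE closed as unresolved has no stop date. If the SAP 6 rule is applied to it, a duration that was only partly observed enters the table as if complete, with a length set by when the subject left the study. Correcting 8.5 does not cure this, because an event closed as chronic or stable also lacks a stop date.

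At stake is the planned duration summary for related TEAEs by SOC and PT in a first-in-human study: its mean, SD and maximum, and the within-subject average of repeat episodes.

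**Working it through.** **Part 1: the follow-up rules, for a related AE open 30 days after last dose**

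- 8.5: follow-up ends; outcome recorded as unresolved.
- Footnotes w/v: if it is ongoing at the post-treatment visit, follow-up continues.
- 5.3: follow-up continues to resolution or permanent sequelae.
- 6.5: status must be assessed, but no length of follow-up is set.

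The direct conflict is 8.5 against the footnotes and 5.3. The visible SAE text applies the 30-day stop to unrelated events only ("In the case where an unrelated SAE has not completely resolved up to 30 days after last dose of study treatment"), which suggests that 8.5 lacks the same qualifier. For a new related AE after day 30, 8.5 captures the event but its own follow-up limit has already passed.

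**Part 2: the duration rule**

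The plan gives no figure to reproduce. Inputs from the documents: duration = stop − start + 1 (SAP 10.2); missing stop = study discontinuation (SAP 6); survival contact for at most 3 years after C1D1 (Protocol 4.1.4); q21d dosing. SAP 8.1 reports treatment and study discontinuation separately, so study discontinuation need not be the EOT visit.

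Assumed, because the documents do not give them: the AE starts on the last dosing day, is open at day 30, and has one record; the dose counts, exit dates and true durations below.

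1. Observed follow-up to day 30: 30 − 0 + 1 = 31 days.
2. Imputed duration with exit at day 30: 31. With exit 183 days after last dose: 183 − 0 + 1 = 184.
3. Ceiling at 3 years. Three years after C1D1 is 1096 days later, study day 1097. Last dose day = 1 + 21 × (doses − 1).
   - 6 doses: day 106; 1097 − 106 + 1 = 992.
   - 17 doses: day 337; 1097 − 337 + 1 = 761.
   - 35 doses: day 715; 1097 − 715 + 1 = 383.
4. Direction, imputed minus true:
   - true 46, exit at 183 days: 184 − 46 = +138.
   - true 401, exit at 183 days: 184 − 401 = −217.
   - true 46, exit at day 30: 31 − 46 = −15.
5. Six subjects with one PT, five resolving in 7 days and one open (value u). Mean = (5 × 7 + u)/6; SD = (u − 7)/√6.
   - imputed u = 184: mean 36.5, SD 72.3.
   - true u = 46: mean 13.5. True u = 401: mean 72.7.
   - median 7 in each case.
6. Three of the six open at 184: median (7 + 184)/2 = 95.5.
7. The median can move with fewer than half open. Take three subjects: two resolved at 3 and 30 days, the third with a true duration of 4 but imputed at 184. The true median is 4; the imputed median is 30.
8. With censoring in the case of step 5 (five events at 7, one censored at 31): S(7) = 1/6, Kaplan-Meier median 7, one of six ongoing.

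Events that outlast study exit are plausible: Protocol 6.10.2 lists as grounds for permanent discontinuation "Grade 2 or 3 immune-related AEs (irAEs) that do not improve to Grade 0 or 1, except endocrinopathies managed with replacement hormones", so it foresees endocrinopathies on replacement therapy.

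**The case against.** The best defence of the SAP is that SAP 6 deals with incomplete data, and a blank stop date on an AE recorded as not resolved is a recorded status, not a missing value. The SAP is silent on ongoing events, so the literal reading is an inference. This stands as a caution, but it does not rescue the rule: the text covers any AE and makes no exception, and if open events were left out they would have no duration and would drop from the summary. The Kaplan-Meier provision in SAP 5 is for time-to-event variables, and AE duration is not named as one.

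Other objections also stand in part. The illustrations depend on assumed exit dates and dose counts; the ceilings need a subject with advanced cancer to stay in follow-up for 3 years. Protocol 8.3 asks for start and stop dates at each severity level, so an event that changes grade may have several records and a smaller average than shown. All AEs are listed by subject, so open events can be traced.

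A reader might infer more than the documents support:

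- *That 6.5 contradicts 8.5.* One assessment at EOT could satisfy 6.5. The visit window ("The EOT/Early Termination visit is to occur within 30 days (+ 10 days) after last dose of study drug") is ordinary tolerance; day-30 status can be recorded at a day-40 visit.
- *That related SAEs are also cut off at 30 days.* The text on related SAEs is not visible, so nothing is claimed about them.
- *That footnotes w/v already cover later-onset AEs.* They reach only events ongoing at the post-treatment visit.
- *That imputation is conservative, or never shorter than what was observed.* It errs in both directions, and if 5.3 follow-up runs past study exit, the imputed date precedes the last observation.
- *That the median is safe while fewer than half are open.* Step 7 shows otherwise.

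**Conclusion.** Both parts hold, and the point is minor. Protocol 8.5 conflicts with footnotes w/v and 5.3, most clearly for non-serious related AEs. SAP 6 with 10.2, read literally, treats open durations of related TEAEs as observed and makes them depend on study exit. The error can go either way and falls mainly on the mean, SD, maximum and within-subject average; the median is usually less affected.

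The size in practice is unknown, because the documents do not say how often related AEs stay open. The figures above are illustrations with one record per event. All analyses are descriptive. DLT counts, the MTD, AE incidence and grade, and ORR do not change.

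**What to change.** **Protocol 8.5.** Limit the 30-day stop to unrelated AEs. Follow related AEs to resolution, stabilisation (chronic or stable) or permanent sequelae, in line with footnotes w/v and 5.3. State the same rule for related AEs with onset after day 30, which 8.5 captures.

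**SAP 6 and 10.2.**

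- Do not impute study discontinuation for related TEAEs unresolved at the last AE assessment. Censor them at that date and report the number ongoing by PT.
- Analyse duration per episode, with a Kaplan-Meier median where numbers allow and a listing of durations otherwise. Alternatively, restrict the within-subject average to completed episodes and report open episodes beside it. A resolved-only summary on its own would not do, because it tends to lose the longest events.
- State how the grade-change records of Protocol 8.3 are joined into one event.

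**Cost.** Wording in two documents, a little extra data entry and analysis, and sparse Kaplan-Meier estimates in small dose cohorts. Sample size, scheduled visits and the primary analyses stay as they are.

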#### **8.6 Serious AE Definition**

An SAE is defined as any untoward medical occurrence that at any dose:

- Results in death
- Is life threatening, i.e., in the opinion of the Investigator, the AE places the subject at immediate risk of death from the event as it occurred; it does not include a reaction that, had it occurred in a more severe form, might have caused death.
- Requires inpatient- hospitalization or prolongation of an existing hospitalization that occurs during the course of a subject's participation in a clinical study, except for those due to the following:
  - A surgery or procedure that was planned before the subject entered the study and which is part of the planned study procedure.
  - Nonmedical reasons, in the absence of an AE.
- Results in persistent or significant disability or incapacity
- Is a congenital anomaly or birth defect
- Is an important medical event that, based upon appropriate medical judgment, may jeopardize the subject and may require medical or surgical intervention to prevent one of the other outcomes listed above

Death is an outcome of an AE, and not an AE in itself. All deaths regardless of causality must be reported. An efficacy failure is not considered an SAE. "Life-threatening" means that the subject was at immediate risk of death from the event as it occurred. This does not include an event that might have led to death, if it had occurred with greater severity. "Inpatient hospitalization" means the subject has been admitted to a hospital for medical reasons for any length of time. The Investigator should attempt to establish a diagnosis of the event based on signs, symptoms, and/or other clinical information. In such cases, the diagnosis will be documented as the AE and/or SAE and not the individual signs/symptoms.

### **8.7 Serious AE Reporting**

SAEs with an onset within 30 days after the subject's last dose of study treatment, but before initiation of a new antineoplastic treatment, will be reported to Nektar Therapeutics Drug Safety within 24 hours of when the site becomes aware of the event. It is anticipated that some patients will experience disease progression before study discontinuation, and the disease progression may result in hospitalization or death. Adverse events leading to hospitalization or death typically are considered serious and require reporting on a serious adverse event form. In addition, disease progression per se is already captured as an efficacy endpoint. Where possible,

- It is unlikely that any additional information can be obtained (e.g., subject or health care practitioner refuses to provide additional information; lost to follow-up after demonstration of due diligence with follow-up efforts)
- The subject dies or is lost to follow-up.

All ongoing SAEs assessed as “unrelated” to study medication will be followed until resolution or until 30 days after last dose of study medication, whichever is earlier. In the case where an unrelated SAE has not completely resolved up to 30 days after last dose of study treatment, the final outcome of these ongoing SAEs will be captured as “Not Recovered/Not Resolved” or “Recovering/Resolving”, whichever is applicable.

### 8.9 Immune-Related Adverse Event Reporting

Immune-related adverse events (irAE) are considered adverse events of special interest due to their potential clinical significance. Investigators should use clinical judgment to determine that an adverse event is immune related, and are encouraged to rule out neoplastic, infectious, metabolic, toxic or other etiologies, to the extent possible, before characterizing an event as immune related.

Grade 3 or higher immune-related adverse events, with an onset within **30 days** after the subject’s last dose of study treatment, must be reported to Nektar Therapeutics Drug Safety or its designee within **24 hours** of when the site becomes aware of the event.

[REDACTED]

[REDACTED]

- [REDACTED]
- [REDACTED]

The Investigator must complete the SAE Form, mark the report as an immune related adverse event and send the completed form via email or fax to Nektar Therapeutics Drug Safety. Any medication or other therapeutic measures used to treat the event will be recorded. A follow-up report will be emailed or faxed to Nektar Therapeutics Drug Safety as soon as additional details become available.

### 8.10 Pregnancy

The sponsor must be notified within 24 hours of the initial report and any follow-up reports of a male subject’s female partner or a female subject becoming pregnant during the course of the

study and for 3 months after the last dose of the study drug. Pregnancy, although reportable, is not considered an AE/SAE unless a female subject or male subject's female partner experiences signs or symptoms of pregnancy complications; however, the contact information for pregnancy reporting is the same as for SAE reporting and listed in Section 8.7. Females who become pregnant will be followed every trimester until the outcome of the pregnancy is known. Pregnancy follow-up should describe the outcome of the pregnancy, including any voluntary or spontaneous termination, details of the birth, and the presence or absence of any congenital abnormalities or birth defects in the offspring.

If a female subject becomes pregnant, administration of the study drug must be discontinued immediately.

### **8.11 Clinical Laboratory Tests**

Clinical laboratory tests will be conducted according to the Schedule of Assessments (Section 1.2). Clinical laboratory tests will be performed by the local laboratory for the Dose Escalation phase and central laboratory for the Dose Expansion phase. Clinical laboratory test data will be reviewed by the Investigator or qualified Sub-investigator. Additional clinical laboratory tests may be ordered at the Investigator's or qualified Sub-investigator's discretion. Additional testing for PK and biomarkers will be performed by the designated central laboratory.

The Investigator or qualified Sub-investigator will review all laboratory results for clinical significance. Any laboratory result deemed clinically significant (i.e., are associated with signs and symptoms, require treatment or require follow-up) will be recorded as an AE as described in Section 8.1.

### **8.12 Vital Signs**

Vital sign measurement will be recorded at every visit. Vital signs include pulse rate, respiratory rate, systolic and diastolic blood pressure, and temperature (oral).

### **8.13 Electrocardiograms**

Five-minute summary ECGs will be performed on a calibrated 12-lead machine according to the Schedule of Assessments (Section 1.2). Subjects must be resting quietly in the supine position for at least 5 minutes before the ECG. ECG recordings will start at 5 minutes before the time point and end at the time point. All ECGs should be recorded before any corresponding PK samples are obtained. Interpretation of ECGs and interval duration measurements will be performed by a designated ECG laboratory. Interpretation of ECGs and interval duration measurements will be provided to the site.

At each time point, 5 minutes of ECG data will be recorded. The 5 minutes of ECG data is converted into a Summary ECG (simulated 10-second ECG) for each subject. The Summary ECG is then submitted to CalECG (version 3.3.0) and the Glasgow algorithm (version 27.0.2) for measurements and diagnoses, and to the Cardiologist over-reader for confirmation, as though it were a standard 10-second ECG.

The Investigator or qualified Sub-investigator will review all ECG interpretations and interval duration measurements for clinical significance. Any ECG interpretation deemed to be clinically significant will be reported as an AE as described in Section 8.1. Subjects who are discontinued will be required to complete the ET visit and all safety follow-up procedures.

